9.7 Safety Analyses

All definitions relative to safety endpoints are detailed in [Section 4.4](#).

All the safety analyses will be performed on the FAS for all safety variables specified below and summarised by cohort/treatment subgroup and overall.

For each safety variable, the last value collected before the first dose of study drug will be used as baseline (i.e., Baseline 2 defined in the table of derived variables in [Appendix A](#)) for all analyses unless otherwise specified.

In addition, different with efficacy analysis, laboratory related safety endpoints will be considered up to 28 days follow-up after the last dose.

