8.1 Handling of Missing Data and/or Invalid Data and Outliers

8.1.1 Missing Data Analysis Methods for Efficacy Endpoints

No imputation will be made for any missing data. The assessments after intercurrent events (death, or initiation of rescue treatments such as biliary diversion surgery or liver transplantation) or follow-up assessments (\geq last dose day + 15 days) will be excluded from analysis with the exception of the analysis of patients undergoing biliary diversion surgery or liver transplantation. For eDiary data analysis, data after last dose will be excluded from analysis.

9. Statistical Methods

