9.7.2 Clinical Laboratory Evaluations

Clinical laboratory test results will be listed.

The following laboratory variables will be analyzed.

- Hematology:
 - Red blood cells and platelets: hemoglobin, hematocrit, red blood cell count, and platelet count
 - White blood cells: white blood cell count, neutrophils, lymphocytes, monocytes, basophils, and eosinophils
- Clinical chemistry:
 - Metabolism: total cholesterol, triglycerides, creatine kinase, albumin
 - Electrolytes: sodium, potassium, chloride, calcium
 - Renal function: creatinine, blood urea nitrogen, estimated glomerular filtration rate
 - Liver function: ALT, AST, Alkaline phosphatase (and isoenzymes as applicable), direct bilirubin, total bilirubin, gamma-glutamyl transferase
 - Pregnancy test: Serum β -human chorionic gonadotropin (all female patients with positive urine pregnancy test)
- Urinalysis:
 - Urinalysis for quantitative analysis: pH, proteins, glucose, blood, ketones, leukocytes, and nitrites
- Other Labs: Vitamin A and E, 25-hydroxy vitamin D, INR, Alfa-fetoprotein (AFP), and Prothrombin Time

❖ Quantitative Analyses

For all laboratory variables above, descriptive statistics for clinical laboratory values (in SI units for all tests, and in conventional units for selected tests ([Appendix F](#)) and absolute changes from baseline at each post-baseline visit ([Appendix B](#)) will be presented. The change to the last visit will also be summarized. Central laboratory data will be used for the summary. If central laboratory data are not available due to COVID-19 or other reasons, local laboratory data will be used, if available.

Change from baseline in ALT, AST, GGT, direct bilirubin, total bilirubin will be summarized by visit using descriptive statistics. Figure of mean (\pm standard error [SE])

changes from baseline 2 will be provided at each available post-baseline visit. The figures will only present results in a treatment group if there's data for at least 5 patients at that visit; if all treatment groups at that visit do not have at least 5 patients' data, that visit will not be presented in the figure.

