Evaluation of drug-induced serious hepatotoxicity (eDISH) plots will be presented for baseline and post-baseline liver function (ALT vs total bilirubin). Baseline eDISH plot will present concurrent levels of baseline ALT vs. total bilirubin as multiples of upper limit of normal (ULN). Post-baseline eDISH plot will present concurrent levels of peak ALT on treatment vs. peak total bilirubin within 30 days of peak ALT as multiples of ULN. In addition, a modified eDISH plot will present concurrent peak ALT vs peak total bilirubin as multiples of individual patient baseline values. Corresponding summary tables will be provided.

❖ Analyses according to reference normal range

Shift tables from baseline to the highest and lowest post-baseline value for quantitative variables will be presented for the clinical laboratory parameters. The laboratory results will be classified as low, normal, and high based on the normal range that was provided by central/local laboratories.

For ALT, AST and total bilirubin, a shift table based on the following classifications (per DILI guidance and CTCAE) will be presented:

- ALT and AST: ≤ 3 ULN, > 3 and ≤ 5 ULN, > 5 and ≤ 10 ULN, > 10 ULN
Total Bilirubin: ≤ 2 ULN and > 2 ULN

❖ Liver Monitoring

Furthermore, a listing of patients meeting the following criteria for liver monitoring will be provided as follows:

- (ALT or AST $\geq 3 \times$ baseline or absolute threshold increase ≥ 300 U/L) and total bilirubin > 2 ULN (normal baseline) at the same visit
- ALT or AST > 5 ULN (normal baseline) or increase ≥ 300 U/L (baseline ALT or AST $>$ ULN) in presence of normal LDH and CPK at the same visit

- INR increased to >1.5 (normal baseline) or increased by >0.4 relative to baseline (abnormal baseline)
- Total bilirubin $\geq 2 \times$ baseline (baseline total bilirubin <3 mg/dL) and total bilirubin is greater than $2 \times$ ULN, or increased by ≥ 3 mg/dL relative to baseline (baseline total bilirubin ≥ 3 mg/dL)

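### Safety laboratory summaries run to last dose + 28 days with no stop at liver transplantation, so a post-transplant value can be compared with the pre-transplant baseline

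*SAP*

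**What the plan says.** - **Efficacy rule.** Section 8.1.1, whose heading confines it to efficacy endpoints, removes assessments made after death or "initiation of rescue treatments such as biliary diversion surgery or liver transplantation) or follow-up assessments" from 15 days after the last dose onward. Section 9.6 accordingly limits laboratory efficacy data to 14 days after the last dose.
- **Safety rule.** Section 9.7 announces a difference from efficacy: "laboratory related safety endpoints will be considered up to 28 days follow-up after the last dose". For each safety variable, "the last value collected before the first dose of study drug will be used as baseline". Neither 9.7 nor 9.7.2 mentions transplantation as an end point for laboratory data.
- **Outputs.** Section 9.7.2 plans "absolute changes from baseline at each post-baseline visit", and adds: "The change to the last visit will also be summarized". It also says: "Shift tables from baseline to the highest and lowest post-baseline value for quantitative variables will be presented", and "For ALT, AST and total bilirubin, a shift table based on the following classifications (per DILI guidance and CTCAE) will be presented". eDISH plots and a liver-monitoring listing follow.
- **Data source.** "Central laboratory data will be used for the summary"; local results are used where central ones are not available.

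**The concern.** Transplantation is an expected event in this trial. It is counted as a secondary endpoint (4.2) and as a disposition category (9.2). ALT, bilirubin or INR measured afterwards describes the graft, while Baseline 2 describes the liver the patient had before the first dose. The difference between the two is not a change on odevixibat. It can go in either direction, so it can hide a liver abnormality or suggest one, in the tables meant to show hepatic safety. The SAP already treats post-transplant values as unsuitable for a comparison with baseline when the endpoint is efficacy, but gives no reason for treating the same comparison differently under safety.

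**Working it through.** The plan gives no figure for this point, so the check sets the rules side by side and follows the day windows.

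**1. Which rule applies**

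| | Efficacy laboratory data | Safety laboratory data |
|---|---|---|
| SAP section | 8.1.1, 9.6 | 9.7 |
| Last day used | last dose + 14 | last dose + 28 |
| After transplantation | excluded | no rule |
| Baseline for liver tests | Baseline 2 (9.6.5) | Baseline 2 (9.7) |

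Section 8.1.1 cannot be carried over to safety. Its heading limits it to efficacy, and the same sentence drops follow-up from day 15, which 9.7 expressly departs from. The other statements of the exclusion (Appendix A and the footnotes to Tables 7 to 10) concern eDiary pruritus measures. Days 15 to 28, that is 28 − 14 = 14 days, count for safety only.

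**2. Can a study sample fall after surgery and inside the window?** Section 3.1 gives prematurely withdrawn patients a Visit 12 at 28 days after the last dose. Table 4 allows ±7 days: 28 − 7 = 21 to 28 + 7 = 35. A visit on days 21 to 28 is inside the safety window and one on days 29 to 35 is outside. Table 4 also keeps a Follow-up window from last dose + 15 to + 28. A patient transplanted between the last dose and such a visit therefore contributes a post-transplant sample.

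**3. Which baseline?** Appendix A fixes Baseline 2 before the first dose in this study and does not reset it. For a patient transplanted after that dose, Baseline 2 is necessarily a pre-transplant value.

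**4. Which outputs are affected?**
- *Change to last visit:* affected whenever the post-transplant sample is the last one kept.
- *Highest/lowest shift tables:* affected when the post-transplant value is the patient's extreme. Visit windows give no protection here.
- *ALT, AST and total bilirubin category shifts:* affected in the same way if the post-baseline category comes from the extreme value.
- *By-visit change:* affected only if the sample is the one closest to the target day. Sections 4.3 and 9.6.5 also summarise ALT, GGT, total bilirubin, INR and liver enzymes as exploratory efficacy variables, so a transplant-excluded version exists. That version ends at last dose + 14, so the safety Follow-up row has no counterpart.
- *Standard eDISH:* peak ALT is limited to treatment, but the paired bilirubin may lie up to 30 days from it, so a post-transplant bilirubin could be paired with a pre-transplant ALT.
- *Modified eDISH:* affected unless it too is read as limited to on-treatment peaks.
- *Liver-monitoring listing:* such values belong there, but need a flag.

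**5. Size.** The planned Cohort 2 size is 60 (Section 5). One patient changes one cell by at most 1/60 = 1.7 points, two by 2/60 = 3.3, three by 3/60 = 5.0. The range of 0 to 3 patients is an assumption with no source in the SAP. Columns of other sizes scale accordingly.

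**The case against.** The strongest reply is that this is a deliberate safety convention. Section 9.7 says openly that safety differs from efficacy, and the 28-day limit matches the treatment-emergent adverse event window in 9.7.1. Reporting everything within a fixed post-dose period is legitimate. That stands as a reason for the longer window and for keeping every value. It does not explain comparing a graft with the patient's earlier liver.

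The route is also narrow. Central results are the default, Visit 12 counts only on days 21 to 28, and later contacts are by telephone. The SAP does not say whether dosing stops at transplantation or whether study blood is drawn afterwards. This stands, and it limits the grade. So does the existence of censored exploratory summaries for most of the by-visit changes.

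A reader can also trace single cases, since laboratory results are listed by patient and date and the DSMB adjudicates hepatic events. That helps interpretation but leaves the tables as they are.

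Finally, a reader might infer that both eDISH plots should use on-treatment values only. The SAP does not support that. The 30-day pairing lets in bilirubin that rises after the drug is stopped, and an on-treatment limit would lose that information for patients who were never transplanted.

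**Conclusion.** The gap is real on the text: no safety rule stops liver-related laboratory summaries at transplantation, and the baseline stays pre-transplant. It matters mainly for the change to last visit, the highest/lowest shifts and the ALT, AST and total bilirubin category shifts.

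Two stronger readings are tempting. One is that the hepatic safety tables are in fact distorted; the SAP gives no number of affected samples, it may be zero, and the 0 to 5.0 point range is only an illustration under an assumed 0 to 3 patients. The other is that the SAP contradicts itself; it does not, because 9.7 declares a separate rule for safety. These safety analyses are descriptive, so no test result changes. This is a minor point and a cheap improvement.

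**What to change.** Add to 9.7 and 9.7.2: *for ALT, AST, GGT, ALP, bilirubin and INR, the summaries, shift tables and eDISH plots use values up to the earlier of last dose + 28 days and the date of liver transplantation.* Otherwise keep the eDISH rule of peak bilirubin within 30 days of peak ALT, with no on-treatment limit on bilirubin. Keep all later values in the laboratory and liver-monitoring listings, flagged as post-transplant. Leave adverse event reporting to last dose + 28 days unchanged.

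The cost is one sentence, one date filter, one listing flag and one footnote. The downside is that an enzyme-elevation adverse event arising after transplantation may have its laboratory value only in the listing; the footnote should say so.

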9.7.1 Adverse Events

All AEs will be classified by Primary SOC and PT according to MedDRA, Version 26.0 or higher.

AEs will be classified as TEAEs and defined as follows:

A TEAE is an AE occurring during the treatment period and within 28 days follow-up after the last dose that a) Has a start date on or after the first dose date of study drug, or b) Has a start date before the date of the first dose date of study drug, but worsened in severity on or after the date of the first dose date of study drug. If an AE started in Study A4250-005 and was ongoing at the time of enrolment in Study A4250-008, the AE will not be considered a TEAE unless it worsens in severity on or after the date of the first dose date of study drug.

AEs with missing start dates, but with stop dates that either overlap with the treatment period or are missing, will be considered TEAEs. A TEAE with missing drug relationship- will be considered as related. A TEAE with missing severity will be

considered as severe. Details for imputing missing or partial start dates of AEs are described in [Appendix D](#).

For counting of the number of AEs, if 2 AE records have the same preferred term and the start date of the 2nd AE is the same as or next day after the end date of the 1st AE, then they will be counted as one AE only.

An overall summary of the incidence of TEAEs (number of patients with any events and number of events, if applicable) will include the following:

- All TEAEs
- Drug-related TEAEs (AE will be defined as drug-related if causality is either probably, possibly, or definitely related)
- Severe TEAEs
- TEAEs leading to study discontinuation
- Serious TEAEs
- Drug-related serious TEAEs
- TEAEs leading to death
- Any hepatic TEAEs
 - a. Any liver-related TEAE (events that, per the Investigator, are considered related to PFIC)
 - b. Any suspected drug-induced liver injury (DILI) TEAEs (as adjudicated by the Data Safety Monitoring Board [DSMB] and defined in [Section 9.7.1.2](#))
 - c. Any TEAE of liver decompensation (as defined in Section 9.7.1.2)
 - d. Drug related hepatic disorders – comprehensive search SMQ (narrow and broad)
- Any Fat-Soluble Vitamin Deficiency TEAEs refractory to clinically recommended vitamin supplementation (as defined in [Section 9.7.1.1](#))
- Any Possible Sequelae of FSV Deficiency TEAEs by SOC and PT (Specified TEAEs with PTs are listed in [Appendix G](#))

- Any Clinically Significant Diarrhoea TEAEs (as defined in [Section 9.7.1.1](#))

TEAEs (number of patients with any events and number of events, if applicable) by SOC and PT in each treatment group will be tabulated for the following:

- TEAEs by SOC and PT including fat-soluble vitamin deficiencies, diarrhoea, hepatotoxicity (as defined in Section 9.7.1.1). Note that hepatotoxicity will also be included with the tabulation of hepatic events
- All TEAEs by preferred term by descending incidence in Overall column
- TEAEs leading to study discontinuation by SOC and PT
- Serious TEAE by SOC and PT
- Drug-related serious TEAE by SOC and PT
- TEAEs leading to death by SOC and PT
- Common TEAEs ($\geq 10\%$ in overall)
- Hepatic TEAEs
 - a. Liver-related TEAEs (events that, per the Investigator, are considered related to PFIC) by SOC and preferred term
 - b. Suspected DILI events (as adjudicated by the DSMB and defined in [Section 9.7.1.2](#))
 - c. TEAEs of liver decompensation (as defined in Section 9.7.1.2) by SOC and preferred term
 - d. Drug related hepatic disorders – comprehensive search SMQ (narrow and broad)

Summary tables for the number of patients with any TEAEs by SOC and PT by severity (mild, moderate, severe) and by causality (related [possibly, probably and definitely] versus unrelated [unlikely and unrelated]), will also be provided during the treatment period. AEs with the worst severity will be used in the by-severity summaries. Similarly, AEs with the worst causality (related to treatment) will be used in the by-causality summaries. If severity or causality is missing, data will be imputed to the worst category.

Where a patient has the same AE, based on PT, reported multiple times in the treatment period, the patient will only be counted once at the PT level in AE frequency tables.

Where a patient has multiple AEs within the same SOC in the treatment period, the patient will only be counted once at the SOC level in AE frequency tables.

In the AE summaries, AEs will be sorted alphabetically by SOC and PT. In addition, the numbers of patients with liver-related mortality, liver-decompensation events, and all-cause mortality will be presented using descriptive statistics. Kaplan-Meier curves may be used for time-to-event data (time taken to experience liver-decompensation event, all-cause mortality, and biliary diversion surgery in weeks).

All AEs (including pre-treatment and post-treatment AEs), serious adverse events (SAEs), and deaths will be listed. Separate listings for AEs leading to dose interruption, AEs listing to dose change, and AEs of Interest (Fat-Soluble Vitamin Deficiency, Diarrhoea, Hepatic AEs, and Possible Sequelae of Fat-Soluble Vitamin Deficiency as defined below) will also be provided.

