Before protocol amendment 6 of the A4250-008 protocol, eligible patients were enrolled into this open-label extension study and treated with a daily dose of odevixibat 120 µg/kg/day for 72 weeks. Patients not tolerating the 120 µg/kg/day dose after a minimum of 1 week had the option to down-titrate to a lower dose (40 µg/kg/day). The patient was to return to the higher dose as soon as deemed appropriate by the investigator. Under protocol amendment 6, patients entering Cohort 2 were to start treatment at 40 µg/kg/day with the possibility to dose escalate to 120 µg/kg/day after 12 weeks if there was no improvement in pruritus based on investigator judgment. The patient could return to the lower dose if the 120 µg/kg/day dose was not tolerated following a minimum of 1 week of treatment. Any dose titration was to be done in consultation with the sponsor Medical Monitor or designee. Patients who wished to continue receiving odevixibat after 72 weeks had the option to remain on treatment in an extension period with visits every 16 weeks until the drug was commercially available, provided continued use was supported by the risk-benefit profile and the patient had not been previously withdrawn or discontinued from the study. In that case the 4-week Follow-up period would not occur.

Patients in Cohort 2 went through a Screening period consisting of 2 clinic visits as follows:

[figure not shown]
- Visit S-1: Screening Visit 1 (Days -56 to -35)
- Visit S-2: Screening Visit 2 (Days -28 to -7)

Patients who did not meet eligibility criteria may have been re-screened after consultation with the Medical Monitor. Patients not fulfilling inclusion/exclusion criteria after 3 attempts were not allowed to rescreen.

All patients were to have a minimum of 12 clinic visits and 6 scheduled telephone contacts (see [Figure 1](#) and [Figure 2](#)) as follows:

- Visit 1: Screening/inclusion visit (Day 1; coincided with Visit 9/End of Treatment (EOT) in Study A4250-005 for patients in Cohort 1. Assessments that were performed at Visit 9/EOT during Study A4250-005 were not to be repeated.)
- Visit 2: Week 4
 - Telephone contact 1: Week 8
- Visit 3: Week 12
 - Telephone contact 2: Week 18
- Visit 4: Week 22
- Visit 5: Week 24
 - Telephone contact 3: Week 30
- Visit 6: Week 36
 - Telephone contact 4: Week 42
- Visit 7: Week 46
- Visit 8: Week 48
 - Telephone contact 5: Week 54
- Visit 9: Week 60
 - Telephone contact 6: Week 66
- Visit 10: Week 70

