- Visit 11: Week 72/optional extension period
- Visit 12: Follow-up visit; Week 76 (for those not participating in optional extension period)
- Optional extension period visits every 16 weeks; Week 88 and onwards

Figure 1 Study Design

[figure not shown]

QD: once daily; T: telephone contact; V: study visit; VS: Visit Screening

Note: Visit 1 coincides with Visit 9 of Study A4250-005. Patients who are not tolerating the 120 µg/kg/day dose may be down-titrated to the 40 µg/kg/day dose following a minimum of 1 week of treatment. The patient can return to the higher dose as soon as deemed appropriate.

This figure is only applicable to Cohort 2 up to Protocol Amendment 5. [Figure 2](#) presents the study design for Cohort 2 as of Protocol Amendment 6.

Figure 2 Study Design for Cohort 2 as of Protocol Amendment 6

QD: once daily; T: telephone contact; V: study visit; VS: Visit Screening

Note: As of Protocol Amendment 6, patients entering Cohort 2 will start treatment at 40 µg/kg/day with the possibility to dose escalate to 120 µg/kg/day after 12 weeks if there is no improvement in pruritus based on investigator judgment. The patient can return to the lower dose if the 120 µg/kg/day dose is not tolerated following a minimum of 1 week of treatment.

Patients were to return to the clinic at Weeks 4 and 12 and thereafter every 10 to 12 weeks for follow-up measurements. Between clinic visits there was to be a telephone contact with the patient and/or caregiver to report AEs. Additional clinic visits may have been required for patients who needed direct site assistance for AE monitoring for safety maintenance and other assessments.

At Visit 11, patients were to be offered the choice to continue receiving odevixibat treatment in an optional extension period. During the optional extension period the patient was to receive odevixibat at the same dose as at the end of the 72-week treatment

period, returning to the clinic every 16 weeks until the drug is commercially available, provided continued use was supported by the risk-benefit profile and the patient had not been previously withdrawn or discontinued from study.

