9.1 General Statistical Conventions

Study data will be reviewed periodically (approximately on a quarterly basis) by a DSMB. For DSMB analyses, the Adjudication Process Document outlines the events that

will be adjudicated and see [Section 9.8.2](#). Descriptive statistics are mainly used in this open-label extension study unless otherwise specified. All statistical procedures will be completed using SAS®, Version 9.4 or higher.

Continuous variables will be summarised using descriptive statistics, including the number of patients with non-missing value (n), mean, median, StdDev (or standard error [SE]), minimum, and maximum. The letter “n” will be presented without a decimal point. Minimum and maximum values will be presented to the same precision as in the database. Mean and median will be presented to 1 more decimal place than the minimum and maximum. StdDev or SE will be presented to 1 more decimal place than the mean and median.

For categorical variables, summaries will include counts of patients (frequencies) and percentages. Percentages will be rounded to 1 decimal place. Descriptive summaries of change from baseline in categorical variables will be provided using shift tables, as applicable.

For summary purposes, if not otherwise specified, the baseline value of a parameter is defined as the last non-missing assessment of that parameter before the first dose of odevixibat in Study A4250-008 ([Appendix A](#)). Derived variables used for the analyses are provided in Appendix A.

Analysis windows defined in [Appendix B](#) will be applied for all laboratory parameters, questionnaires, vital sign measurements, physical examinations, and other efficacy parameters in the study, unless otherwise specified.

For the final CSR, all summaries will be presented for the following treatment groups, unless otherwise specified.

- Placebo (A4250-005) to Odevixibat (A4250-008)
- Odevixibat 40 or 120 µg/kg/day (A4250-005) to Odevixibat 120 µg/kg/day (A4250-008)
- Cohort 2 (A4250-008)
- Odevixibat Overall

Table header will be presented as follows:

Placebo/Odevixibat ^a (A4250-005/A4250-008)	Odevixibat/Odevixibat ^b (A4250-005/A4250-008)	Cohort 2 ^c (A4250-008)	Odevixibat Overall
--	---	--------------------------------------	-----------------------

a Includes patients who received placebo in Study A4250-005 and transitioned to odevixibat 120 µg/kg/day in Study A4250-008

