9.2 Patient Disposition

All patients who provided informed consent will be included in a summary of patient accountability.

The following categories will be summarised by cohort/treatment subgroup and overall as follows:

- Patients screened
- Screening failures
- Patients eligible to receive dose
- Patients dosed
- Patients completing 72 weeks treatment period
 - Patients not enrolled in optional extension treatment period
 - Patients enrolled in the optional extension treatment period
 - Patients ongoing in optional extension treatment period

- Patients discontinuing optional extension treatment period (including reasons for treatment discontinuation)
- Patients discontinuing 72 weeks treatment period early (including reasons for treatment discontinuation)
- Patients who have undergone biliary diversion surgery
- Patients who have undergone liver transplantation
- Patients who have been listed for liver transplantation

Additionally, analysis populations will be summarised overall and by region ([Appendix C](#)).

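### TEAE percentages are crude counts over a window that includes an open-ended extension, so they have no defined time frame and mix risk with length of follow-up

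*SAP*

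**What the plan says.** **Window.** SAP section 9.7.1: "A TEAE is an AE occurring during the treatment period and within 28 days follow-up after the last dose". Appendix A repeats the definition. Neither place sets an upper limit in study days.

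**Extension.** Section 3.1 lets patients who finish 72 weeks "remain on treatment in an extension period with visits every 16 weeks until the drug was commercially available". Section 9.2 treats this as treatment, with a disposition category "Patients discontinuing optional extension treatment period" and another for patients still ongoing in it.

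**Measure.** Section 9.7.1: "TEAEs (number of patients with any events and number of events, if applicable) by SOC and PT in each treatment group will be tabulated". Section 9.1 supplies the percentage: "For categorical variables, summaries will include counts of patients (frequencies) and percentages".

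**Columns.** Section 9.7 has all safety variables "summarised by cohort/treatment subgroup and overall". In the final report these are Placebo/Odevixibat, Odevixibat/Odevixibat, Cohort 2 and Overall (section 9.1). Section 9.7.1 also plans a table of common TEAEs, defined by a 10% threshold in Overall.

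**What else touches time.** Section 9.5.1 summarises treatment duration by the same columns, separately from the AE tables. Section 9.7.1 allows, but does not require, Kaplan-Meier curves for liver decompensation, all-cause mortality and biliary diversion. Section 9.6.4 evaluates surgery and transplantation at Weeks 24, 48, 72 and each extension visit, with Kaplan-Meier where appropriate and censoring at last contact.

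**The concern.** A percentage of patients with an event is interpretable as a risk only if one knows over what period. Here the period is each patient's own time on drug plus 28 days. That time has no planned end for anyone who takes the extension. A patient who leaves at Week 72 is observed for about 76 weeks, while one who stays is observed for as long as supply continues.

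Evaluating long-term safety is a secondary objective (section 2.2), and section 4.4 makes TEAE incidence the primary safety analysis. Three displays are affected: the percentage in each column, the percentage in Overall, and the list of common TEAEs, whose membership depends on how long patients happened to be followed. If follow-up also differs between columns, the side-by-side percentages would differ even if the hazard were the same in all of them.

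The plan handles time for surgery and transplantation and windows its laboratory data through the extension. The TEAE tables are where unequal follow-up is pooled into one percentage.

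**Working it through.** **1. Is the extension inside the TEAE window?** Section 9.7.1 does not define the treatment period. Two things indicate that the extension is included: the window is anchored to the last dose, and section 9.2 names the extension as a treatment period. If only the 72 weeks counted, an AE early in a long extension would fall outside the definition while one shortly after the final extension dose would fall inside it, which is hardly intended.

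**2. Is there a person-time rate, common cut-off or extension split for TEAEs?** None appears in sections 4.4, 9.5.1, 9.7 or 9.7.1, the list of changes in section 10, or Appendix A.

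**3. Is there a figure in the plan to reproduce?** No. The SAP states neither an expected TEAE rate nor the follow-up per column. The sizes below rest on assumed inputs and are illustrations.

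**4. Illustration A: risk fixed at Week 76.** Assumptions: constant hazard, no drop-out, and a window of 72 + 4 = 76 weeks without extension or 76 + *e* weeks with *e* extension weeks.

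- Share of observation time beyond 76 weeks = *e* / (76 + *e*)
- Crude risk = 1 − (1 − p)^((76 + *e*)/76), with p the risk by Week 76

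| Extension weeks *e* | Window (weeks) | Share beyond Week 76 | Crude risk, p = 10% |
|---|---|---|---|
| 0 | 76 | 0% | 10.0% |
| 16 | 92 | 17% | 12.0% |
| 32 | 108 | 30% | 13.9% |
| 64 | 140 | 46% | 17.6% |
| 104 | 180 | 58% | 22.1% |

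For the 10% list, p = 8% with 32 extension weeks gives 1 − 0.92^(108/76) = 11.2%, so the event crosses the threshold. Each row assumes every patient has the full extension; a real column is a mixture and would lie in between.

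**5. Illustration B: same rate, different follow-up.** Crude risk = 1 − exp(−rate × weeks/52).

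| First events per 100 patient-years | 72 weeks | 104 weeks | 200 weeks | Ratio, 200 to 72 |
|---|---|---|---|---|
| 5 | 6.7% | 9.5% | 17.5% | 2.6 |
| 10 | 12.9% | 18.1% | 31.9% | 2.5 |
| 20 | 24.2% | 33.0% | 53.7% | 2.2 |
| 50 | 50.0% | 63.2% | 85.4% | 1.7 |

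**6. Does the proposed change remove this?** At 20 per 100 patient-years, the exposure-adjusted rate is 20 in every column whatever the follow-up. A crude percentage over a common 72 weeks is 24.2% in every column.

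**7. Contact density.** Visits 2 to 11 are 10 clinic visits in 72 weeks, or 10 × 52/72 = 7.2 a year, plus 6 telephone contacts. In the extension, visits every 16 weeks are 52/16 = 3.25 a year. If AEs are captured less completely there, illustrations A and B overstate the growth in recorded percentages, and a rate per patient-year would understate harm in a column with much extension time.

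**The case against.** The strongest reply is that the study is descriptive. Section 5 rules out formal hypothesis testing, section 9.6.1 says the same of the efficacy methods, and no contrast of TEAEs between columns is planned. The columns are non-randomised and differ in population, earlier odevixibat exposure and, from Amendment 6, starting dose, so adjusting for exposure would not make them comparable. The treatment-duration table lets a reader see an imbalance, and all AEs are listed. This stands as far as it goes: nothing here biases a test. It does not answer the point about Overall and the common list, which lack a time frame even if the columns are balanced. A separate duration table does not let a reader convert a percentage into a rate.

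A second reply is that Kaplan-Meier curves are foreseen. In the safety section they are optional and cover three outcomes, so the general TEAE tables are untouched.

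A reader might go further and infer that Cohort 2 has shorter follow-up because it was still enrolling under Amendment 6, that availability differs by country, and that the Cohort 1 columns will therefore look more harmful for reasons unrelated to the drug. The documents do not support this. They give no enrolment dates or follow-up by column. Cohort 2 existed before Amendment 6, and the two Cohort 1 columns come from the same parent study and may be similar. Extension time is also time on odevixibat, so extra events may reflect cumulative exposure, which a long-term study is meant to detect. Equal hazard is the assumption of the illustration, not a finding.

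**Conclusion.** The point holds as a weakness in how the primary safety measure is presented. TEAE percentages and event counts accumulate over a window with no fixed end, and no TEAE table relates them to time at risk. Each column, Overall and the 10% list therefore mix risk with length of follow-up.

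The size in this trial cannot be stated. Under a constant hazard with complete follow-up and ascertainment, a 10% risk by Week 76 would show as 12.0% to 22.1% with 16 to 104 extension weeks. Whether any column is advantaged, and which, is unknown. The TEAE definition is not itself an error, and the plan makes no invalid comparison. The conclusion depends on reading the extension as part of the treatment period, which the last-dose anchor and section 9.2 support but section 9.7.1 does not spell out.

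**What to change.** In section 9.7.1, state that the treatment period includes the extension, and keep the crude tables. For the overall TEAE summary and the SOC/PT, serious, drug-related, hepatic and clinically significant diarrhoea tables, add:

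1. Patients with a first event per 100 patient-years at risk, by column and overall. Person-time ends at the first event or at last dose + 28 days (or at the data cut-off for anyone still on treatment).
2. A TEAE summary limited to onset up to Day 504, or last dose + 28 days if earlier, with extension-period events shown separately.

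Label both as descriptive, with a footnote that the columns are non-randomised and differ in prior exposure and starting dose. Neither addition removes those differences, including up to 24 weeks of earlier odevixibat in the Odevixibat/Odevixibat column.

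The cost is SAP wording and more outputs, all from AE and dosing dates already collected. The rates assume a roughly constant hazard and may understate harm if ascertainment is thinner at 16-weekly visits. The fixed-window table does not rely on either condition, so the two should be presented together.
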